4.5.2. Adverse Events

All AEs will be coded using the MedDRA coding system (version 25.0 or higher) and displayed in tables and in data listings using system organ class (SOC) and preferred term (PT). AE Grade assessment will be based on Investigator reporting using the National Cancer Institute Common Terminology Criteria for Adverse Events [NCI CTCAE], version 4.03.

Summarization will focus on incidence of drug product related AEs, treatment-emergent SAEs by SOC and PT,

A by-subject listing for the following AEs that occurred on extension study will also be provided: drug product-related AEs, treatment-emergent SAEs, drug product-related SAEs, deaths, AEs leading to study withdrawal, and subject deaths. Adverse event listings will be sorted by index study.

4.5.3. Injection Site Evaluations

Injection site evaluations will be measured as shown in the SOA (Table 1-2) and will be summarized by visit according to severity (none, mild, moderate, severe) and type of reaction: erythema, edema, induration, itching, pain or tenderness, or other reaction. For subjects reporting more than one occurrence of the same type of reaction, the most severe reaction will be used for the summary.

A by-subject listing will be provided for all injection site evaluations and will also include measurement (if applicable).

4.5.4. Laboratory Data

Clinical laboratory values will be expressed using the International System of Units (SI). Values will be summarized using raw, change and percent change from extension study baseline for

each clinical laboratory parameter. Clinical laboratory parameters include hematology, chemistry, and urinalysis.

Shift tables, which will indicate abnormally high or abnormally low changes in laboratory parameter grade based on CTCAE criteria from extension study baseline through extension study follow-up, will be performed by visit.

By-subject listings will be provided for all laboratory data collected, including hematology, chemistry, urinalysis, and pregnancy tests.

4.5.5. Concomitant Medications and Procedures

Prior and concomitant medications will be coded using the WHO Drug Dictionary. Concomitant medications are those which were ongoing or began after the patient began participating in the extension trial.

The use of concomitant medications during the extension study will be included in a summary table. Prior and concomitant procedures will be included in a by-subject data listing.

Concomitant procedures will be included in a by-subject data listing.

4.5.6. 12-Lead Electrocardiogram

Electrocardiogram results will be summarized in a by-visit shift table, including the number and percentage of subjects with normal, abnormal, and clinically significant abnormal results at extension study baseline and shift to each extension study visit.

Electrocardiogram data for each subject, including heart rate, PR interval, QRS interval, QT interval, and QTcF interval, as well as the overall interpretation, will be provided in a summary table and a data listing.

4.5.7. Quantitative Skin Color Measurement

Quantitative skin color measurement data will be provided in a by-patient listing.

4.5.8. Bone Age Assessment

Bone age assessment will be measured as shown in the SOA (Table 1-2) if done in the index study. A by-subject listing, including the date of the assessment and result, will be provided as available.

4.5.9.

4.5.10. Vital Signs

Vital signs will be measured as shown in the SOA (Table 1-2). Aside from those used in exploratory evaluation, the raw, change and percent change from extension study baseline of additional vital signs of temperature, heart rate, systolic blood pressure, diastolic blood pressure, respiratory rate will be summarized descriptively by visit. A by-subject listing of all vital signs will be provided.

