4.2.1. Inclusion Criteria

- 1. Patients aged 2 or older (or aged >2 years as per local regulations; ; only patients aged 12 years or older may be enrolled in the trial in Greece; only patients 6 years or older may be enrolled in the trial in Germany) who have completed participation in a previous setmelanotide clinical trial.
- 2. If patient received setmelanotide on an open-label basis in a previous setmelanotide clinical trial, patient demonstrated adequate safety and meaningful clinical benefit (efficacy) in the previous setmelanotide trial. Meaningful clinical benefit is defined as follows:
 - Patients 18 years of age or younger that have completed participation on active drug and demonstrated adequate safety and at least 3% BMI reduction or reduction in BMI Z-score of 0.2 compared to baseline.
 - Patients over 18 years of age should show reduction of 3% BMI compared to baseline.

If the patient participated in a double-blind basis in the previous placebo-controlled clinical trial, patient tolerated blinded study drug.

- 3. Patient and/or parent or guardian is able to communicate well with the investigator, to understand and comply with the requirements of the trial, and to understand and sign the written informed consent/assent. The patient must consent/assent to participate in the trial.
- 4. Patient must meet one of the following requirements regarding contraception:
 - If a female of childbearing potential, defined as fertile, following menarche and until becoming post-menopausal unless permanently sterile (hysterectomy, bilateral salpingectomy, or bilateral oophorectomy), must use a highly effective form of contraception as outlined in Section 6.2.1.
 - If a female of non-childbearing potential, defined as permanently sterile (status post hysterectomy, bilateral oophorectomy, or bilateral salpingectomy) or postmenopausal for at least 12 months (and confirmed with a screening folliclestimulating hormone (FSH) level in the post-menopausal laboratory range), contraception is not required during the trial.
 - Younger female patients who have not reached menarche upon trial entry will be assessed for Tanner staging and at first menarche will be required to comply with contraception requirements and pregnancy testing as outlined in the protocol.

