11.4.2. Bedside Schwartz Equation

In patients, <18 years of age, the Bedside Schwartz Equation should be used as follows:

GFR (mL/min/1.73 m²) = $(0.41 \times \text{height in centimeters})$ / creatinine in mg/dL

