3.5. Methods of Pooling Data

For safety-related analyses, data will be pooled across index studies and rare genetic disorders of obesity and summarized together. For non-safety-related analyses, data will be pooled by rare genetic disorder of obesity within study, as applicable, and data will therefore be summarized by index study.

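### Vital signs and laboratory values are pooled over all ages from 2 upward as raw change for up to 7 years, so growth cannot be separated from drug effect

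*SAP*

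**What the plan says.** Changes in vital signs and laboratory evaluations belong to the primary endpoint (Protocol 2.2.1, SAP 1.4.1).

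- **Vital signs.** SAP 4.5.10 reports by visit "the raw, change and percent change from extension study baseline of additional vital signs of temperature, heart rate, systolic blood pressure", then diastolic pressure and respiratory rate, plus a listing. SAP 3.2 makes this n, mean, median, SD, minimum and maximum.
- **Laboratory values.** SAP 4.5.4: "Values will be summarized using raw, change and percent change from extension study baseline". The same section adds "Shift tables, which will indicate abnormally high or abnormally low changes in laboratory parameter grade based on CTCAE criteria from extension study baseline", by visit. Protocol 8.4 also tabulates how many patients have abnormal results.
- **Pooling.** SAP 3.5: "For safety-related analyses, data will be pooled across index studies and rare genetic disorders of obesity and summarized together". SAP 3.8 defines no subpopulations, and SAP 3.6 plans no covariate adjustment.
- **Age and duration.** Protocol 4.2.1 admits "Patients aged 2 or older", with higher limits in two countries. Follow-up is up to 7 years, and the last treatment visit starts at week 356.
- **Renal function.** Protocol 11.4.2 computes GFR under age 18 as 0.41 × height in cm, divided by "creatinine in mg/dL". Protocol 11.4.1 uses the MDRD equation from age 18. SAP 4.5.4 names no eGFR.
- **Bone age.** SAP 4.5.8: "A by-subject listing, including the date of the assessment and result, will be provided as available".

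For weight the SAP does allow for growth: SAP 3.4 names BMI z-score and percent of the BMI 95th percentile, and a surviving part of SAP 4.3 gives a separate summary for patients over 18.

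**The concern.** Over several years a child's heart rate and respiratory rate can be expected to fall, and blood pressure and creatinine to rise, without any drug. An adult shows little of this. A pooled mean change from extension baseline adds the two groups together. With a single arm there is no control group from which growth could be subtracted.

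If the drug raised heart rate slightly in everyone, the children's falling values would pull the pooled mean toward zero or below it. Growth-related rises in blood pressure and creatinine would push their pooled means up and resemble harm. In either case, a reader of the long-term table could not tell how much of the change came from growth.

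**Working it through.** The plan states no sample size, power or effect size, so there is no figure to reproduce. The two checks below are illustrations.

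**1. Heart rate**

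Inputs from the documents: entry from age 2. Week 356 lies 355 × 7 / 365.25 = 6.8 years after week 1. SAP Table 1-1 counts 9 + 13 + 119 + 12 + 38 + 14 + 1 = 206 patients and gives no ages.

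Assumed, not in the documents: share of growing children 20–60%; growth-related heart-rate change −1 to −3 bpm per year, constant over time; a true drug effect of +3 bpm in every patient; no differential dropout.

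Pooled mean change = share × yearly drift × years + drug effect.

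| Share, drift per year | 1 year | 3 years | 6.8 years |
|---|---|---|---|
| 20%, −1 | −0.2 + 3 = +2.8 | −0.6 + 3 = +2.4 | −1.4 + 3 = +1.6 |
| 40%, −2 | −0.8 + 3 = +2.2 | −2.4 + 3 = +0.6 | −5.4 + 3 = −2.4 |
| 60%, −3 | −1.8 + 3 = +1.2 | −5.4 + 3 = −2.4 | −12.2 + 3 = −9.2 |

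In the middle row the pooled change reaches zero after 3 / (0.4 × 2) = 3.75 years. The 6.8-year column is an upper bound, because it keeps every child drifting for the whole period, including adolescents near adult values.

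A table split by age at extension baseline would show +3 in the adult stratum. The paediatric strata would show +3 plus drift, so the split isolates growth in the children but does not remove it.

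**2. Creatinine**

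Protocol 11.4.2 rearranged: creatinine = 0.41 × height / GFR. At constant GFR the creatinine ratio equals the height ratio, and the 0.41 cancels. The heights are assumptions.

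- 120 to 160 cm at GFR 100: 0.492 to 0.656 mg/dL, 160/120 = 1.33, so +33%. Read without height, this looks like a GFR fall of 1 − 120/160 = 25%.
- Range: 150 to 165 cm gives +10%; 90 to 130 cm gives +44%.
- Contribution to the pooled mean percent change if 40% of patients grow this way: 0.4 × 10 = 4 points to 0.4 × 44.4 = 18 points.

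Height-based eGFR would show 0% change in each case.

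**3. The switch of equation at 18**

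Assumed patients aged 18, without the 1.210 factor, creatinine unchanged:

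- Male, 170 cm, 0.8 mg/dL. Schwartz: 0.41 × 170 / 0.8 = 87. MDRD: 175 × 0.8^−1.154 × 18^−0.203 = 126. Change +45%.
- Female, 160 cm, 0.7 mg/dL. Schwartz: 0.41 × 160 / 0.7 = 94. MDRD: 175 × 0.7^−1.154 × 18^−0.203 × 0.742 = 109. Change +16%.

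An eGFR summary that follows Appendix 11.4 across the 18th birthday would thus create an artefact of its own.

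**The case against.** **Pooled change is not the only report.** Laboratory values also get CTCAE-grade shift tables and abnormality counts. SAP 4.5.6 gives a by-visit ECG shift table and summarises ECG heart rate. Protocol 7.2 makes any clinically relevant deterioration in laboratory or other clinical findings an adverse event. An individual harm therefore has routes that do not depend on a pooled mean. This stands and narrows the point for laboratory values, although the SAP does not say whether age-specific limits apply. Vital signs have no shift or abnormality table.

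**The size is assumed.** This stands. An entry floor of age 2 does not show how many young children enrolled. With a 30–50% share and −2 to −3 bpm per year, the growth-only shift at 1 year is 0.3 × (−2) = −0.6 to 0.5 × (−3) = −1.5 bpm. Creatinine depends on height by the protocol's equation; that cannot be extended to every analyte.

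**Withheld text may contain age handling.** SAP 4.5.9 and much of 4.3 cannot be read, and a surviving fragment splits at 18, so SAP 3.8 does not exclude age splits elsewhere. SAP 3.5, 4.5.4 and 4.5.10 are readable, however, and show none for these data.

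**Stronger readings that the documents do not support.**

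- A reader might infer that growth will be reported as a drug effect. The SAP attributes no change to drug: the trial is single-arm, and SAP 3.7 calls the interpretation descriptive.
- A reader might infer that pooling hides a renal signal. Growth raises creatinine, so it mainly imitates one; it hides one only if a true rise is dismissed as growth.
- A reader might infer that no pooled change can be interpreted in size or sign. That depends on an unknown age mix and does not apply to early visits.

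**Conclusion.** The point holds as a limit on interpretation. Followed as written, the readable plan mixes growth with any drug effect in two components of the primary endpoint, most seriously for vital signs at late visits.

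The proportionality of creatinine to height follows from the protocol's own equation; the +33% example rests on assumed heights. The direction of the heart-rate masking rests on the assumption that heart rate falls with growth, and its size on assumed child share and drift. On those assumptions a uniform +3 bpm effect appears at 3 years as anything from +2.4 to −2.4 bpm. The actual size cannot be known until the age distribution is tabulated.

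Bone age is a lesser matter of presentation. It is not named in the primary endpoint and is continued only where the index trial assessed it.

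**What to change.** 1. In SAP 4.5.4 and 4.5.10, add by-visit summaries by age at extension baseline (under 12, 12–17, 18 and over) beside the pooled table. The protocol already uses cuts at 12 and 18. The adult stratum is then largely free of growth.
2. For patients under 18 at extension baseline, add creatinine as height-based eGFR by Appendix 11.4.2. Do not compute change across the switch at 18: either stop the eGFR change summary there, or keep one equation per patient and record this as a departure from the appendix.
3. State that age-specific reference limits are used for laboratory abnormality flags.
4. Optionally, add age-referenced blood pressure and heart rate for patients under 18, naming the external reference, since the documents contain none. This matters because a single band under 12 still mixes ages 2 to 11.
5. Optionally, show chronological age beside each result in the bone-age listing.

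No new visit or procedure is needed: height is measured at every visit under age 21, and age, year of birth and gender are recorded (Protocol 6.4.2 and 6.4.6). The cost is SAP wording, programming, more tables and smaller cells per age band. The optional age-referenced measures also need a reference to be chosen and programmed.

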4.5.11. Physical Exam and Comprehensive Skin Examination

Physical exams will be measured as shown in the SOA (Table 1-2). Results from each component of the physical exam will be provided in shift tables, summarizing the shift from extension study baseline by visit. A by-subject listing of all physical exam findings will be provided; results of the comprehensive skin examination will be provided in the listing.

Tanner Staging will be presented in a by-subject listing.

4.5.12. Anti-RM Antibody

Anti-RM Antibody will be measured as shown in the SOA (Table 1-2). A by-subject listing, including the date of the assessment and result, will be provided.

Rhythm Pharmaceuticals, Inc. Statistical Analysis Plan, Protocol RM-493-022 June 28, 2024 Version 2.0

7. APPENDIX
